## 3.2 PRIMARY ENDPOINT

The trial is designed as a non-inferiority trial to evaluate whether the Sweetch dDPP is at least as effective as hDPPs on participant attainment of the CDC's benchmark for type 2 diabetes risk reduction, defined as one or more of the following:

- At least 5% weight loss by 12 months
- At least 4% weight loss at 12 months and at least 150 minutes/week of physical activity measured using monthly serial Actigraphy and averaged over months 1-11)
- At least a 0.2% reduction in hemoglobin A1C by 12 months (for participants whose A1C result obtained at baseline study visit is between 5.7% and 6.4%).

Thus, the prospectively defined primary endpoint will be a binary endpoint at 12 months, defined as 1 if at least one of the CDC "success" outcome measures is achieved and 0 if none are achieved. The primary endpoint was selected to align with the current CDC standards for full recognition of DPP programs (effective May, 2021). According to the CDC, participants may demonstrate type 2 diabetes risk reduction by fulfilling one or more of the above outcomes, and, given the broad range of eligibility criteria for the DPP (see Section 5.1), not all DPP participants are eligible to demonstrate success using each of three outcomes in our composite endpoint. Specifically, the A1C change measure can only be used for participants whose baseline measure is in the prediabetic range of 5.7% to 6.4%. These standards require that at least 60% of participants in a given DPP meet the endpoint for attainment of full recognition in order to become a Medicare DPP supplier. The CDC's Standards and Operating Procedures are subject to change during the course of the study. Should the benchmarks for type 2 diabetes risk reduction change prior to completion of the trial, to the extent possible (i.e. assuming we have collected required data during the trial), we will also analyze our outcomes to align with the updated benchmark.

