### 9 STATISTICAL CONSIDERATIONS

## 9.1 STATISTICAL HYPOTHESES

This non-inferiority trial is designed to demonstrate that the Sweetch fully automated dDPP is no worse than the standard of care hDPP with respect to participant attainment of the CDC's benchmark for type 2 diabetes risk reduction. We will assume a percentage of "success" (i.e. attainment of the binary composite endpoint) in both the dDPP and hDPP of 50% and an equivalence limit,  $d$ , of 15%.

The percentage of participants that meet the primary endpoint will be compared between the two randomized groups. The null hypothesis is that the percentage for those in the standard treatment hDPP ( $\pi_s$ ) is better than the percentage on the experimental fully automated treatment dDPP ( $\pi_e$ ) by 15 or more percentage points, versus the alternative that the percentage for those on the new treatment is  $\pi_s - 15$  or better, i.e.

$$H_0: \pi_s \geq \pi_e + 15$$

$$H_a: \pi_s - 15 < \pi_e$$

In selecting the equivalence margin for this non-inferiority trial, we considered the guidance provided by the U.S. FDA. As we seek to evaluate a composite endpoint that has not previously been evaluated in a RCT, our assumptions are based mainly on the primary endpoint of the 5% weight loss outcome at 12 months (one of the three endpoints in our composite endpoint). Weight loss has been shown to be the most significant driver of type 2 diabetes risk reduction. In the landmark DPP trial, the risk difference in attainment of 5% weight loss at 12 months among participants randomized to the intensive lifestyle intervention (active control in the present trial) vs. placebo was 46.7% (95% CI 43.1% - 50.2%). Thus, the fraction of our equivalence margin to the entire effect of the active control is ~32%, which is significantly less than the recommended 50% threshold suggested by the FDA.

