Considering the low rates of referral and retention in the hDPP, a 15% difference in the primary endpoint would be considered acceptable in our clinical judgment in order to gain the advantages of a cheaper and scalable alternative to the current available intervention. In addition, there is significant variability in outcomes attained in real-world DPPs to justify this equivalence margin. Among a subset of hDPPs participating in our study (N=5), the proportion of completers achieving the 5% weight loss outcome was 50% (range 47% to 60%) and the 4% weight loss and 150 minutes of PA outcome was 50% (range 29% to 80%) (unpublished data). Of note, however, the outcomes reported by hDPP are calculated based on program completers (per protocol analysis). In our trial, we plan on conducting an intent-to-treat analysis. Thus, we expect that the observed  $\pi_s$  will be closer to the 30-40% range based on participant-level data across the U.S. from the CDC's national DPP.

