## 9.2 SAMPLE SIZE DETERMINATION

Under a 1:1 randomization design, with a significance level (alpha) of 5% and 80% power, and assuming 50% of the participants achieve the primary outcome in both arms, 138 participants are required to enroll in each of the two arms, for a total study sample size of  $n = 276$ . Assuming a conservative attrition rate of 25% at 12 months, the adjusted sample size is set to 184 per group (368 total) to ensure the minimal necessary analyzable sample of 276 is retained. If there is truly no difference between the hDPP and dDPP, then 276 participants are required to be 80% sure that the upper limit of a one-sided 95% confidence interval will exclude a difference in favor of the hDPP of more than 15%. While it was previously noted that  $\pi_s$  will be closer to the 30-40% range, we used 50% in the non-inferiority sample size calculations as this choice yields the largest necessary sample size among all choices for  $\pi_s$ , and thus makes the study robust, in terms of statistical power, to other values for  $\pi_s$ .

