## 9.3 POPULATIONS FOR ANALYSES

Consistent with the **intention-to-treat (ITT)** principle, results of all study participants will be evaluated according to initial randomization regardless of whether they adhered to their assigned treatment and regardless of protocol violations or deviations. Analyses of effectiveness endpoints, however, will exclude participants who withdraw from the study or withdraw consent. Effectiveness analyses will be performed for the ITT population. All primary statistical analyses of effectiveness measures will be unadjusted and two-sided tests of significance will be used. A per-protocol analysis will also be conducted using the population of program completers in each group, as defined in Section 3.3, to benchmark outcomes against CDC standards.

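### Section 9.3 calls for two-sided tests in all primary analyses, against the one-sided 95% limit and 15-point margin in 9.1 and 9.2, and the primary analysis section does not restate that rule

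*Combined protocol and SAP*

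**What the plan says.** Section 3.2 states the purpose: "The trial is designed as a non-inferiority trial to evaluate whether the Sweetch dDPP is at least as effective as hDPPs". Section 9.1 fixes the scale: "The percentage of participants that meet the primary endpoint will be compared between the two randomized groups". The null there is that hDPP beats dDPP "by 15 or more percentage points, versus the alternative that the percentage for those on the new treatment is" no more than 15 points below hDPP, or better.

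Section 9.2 sizes the trial "with a significance level (alpha) of 5% and 80% power, and assuming 50% of the participants achieve the primary outcome in both arms". It describes the result as being 80% sure that "the upper limit of a one-sided 95% confidence interval will exclude a difference in favor of the hDPP of more than 15" percentage points. This gives 138 evaluable per arm. "Assuming a conservative attrition rate of 25% at 12 months", it becomes 184 randomised per arm.

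Section 9.3 then says: "All primary statistical analyses of effectiveness measures will be unadjusted and two-sided tests of significance will be used". No significance level is attached, and the non-inferiority test is not excepted.

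Section 9.4.1 evaluates primary and secondary outcomes with mixed-effects logistic regression, to allow for clustering within program sites. Section 9.4.7 analyses the primary endpoint with logistic regression on treatment group and names no random effect. Neither mentions a risk difference, a confidence limit, a confidence level or the 15 points.

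**The concern.** The primary endpoint is an effectiveness measure, so the 9.3 sentence covers it as written. It conflicts with the one-sided rule on which the sample size rests. The sections that should instruct the primary analysis do not settle which rule applies, on what scale, or from which model.

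The trial's main conclusion is at stake. An analyst following 9.2 and one joining 9.3 to a conventional 5% level would compute different upper limits from the same data, and could disagree on whether non-inferiority was shown. Section 6.4 makes the trial open-label with an unmasked biostatistician, so this choice should be closed in writing beforehand.

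**Working it through.** **Inputs.** Margin 15 points (9.1); alpha 5%, power 80%, 50% success in both arms, 25% attrition, one-sided 95% limit (all 9.2). Section 9.1 also says the hDPP success rate "will be closer to the 30-40% range based on participant-level data across the U.S. from the CDC's national DPP", so 30%, 35% and 40% are shown too. Participants are treated as independent, as the sample-size calculation implies.

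**Reproducing the plan's figure.** n per arm = (z + 0.8416)² × 2p(1−p) / 0.15².
- One-sided 5% (z = 1.645), p = 0.5: 137.4, so 138; and 138/0.75 = 184. Both match the plan.
- One-sided 2.5% (z = 1.960, the upper limit of a two-sided 95% interval), p = 0.5: 174.4, so 175. This does not match.
- Tests of equality, 50% versus 35%, give 170 (two-sided), 183 (two-sided, continuity-corrected) or 134 (one-sided). None gives 138.

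**Power under each reading.** Power = Φ(0.15/√(2p(1−p)/n) − z).

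| Success, both arms | 9.2 rule, n = 138 | Two-sided 95% CI, n = 138 | Two-sided 95% CI, n = 184 | Evaluable per arm for 80%, two-sided 95% CI | Attrition allowed from 184 |
|---|---|---|---|---|---|
| 50% | 80.2% | 70.3% | 82.1% | 175 | 4.9% |
| 40% | 81.6% | 72.0% | 83.6% | 168 | 8.7% |
| 35% | 83.3% | 74.3% | 85.5% | 159 | 13.6% |
| 30% | 85.9% | 77.6% | 88.1% | 147 | 20.1% |

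The last column is 1 − n/184. The two-sided columns assume that 9.3 is read with a 5% level, which 9.3 does not state.

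**Same data, two answers.** hDPP 69/138 (50.0%), dDPP 63/138 (45.7%): difference 4.3 points, standard error √(0.5×0.5/138 + 0.4565×0.5435/138) = 6.01 points.
- Under 9.2: 4.35 + 1.645 × 6.01 = 14.2, below 15, so non-inferiority is met.
- Under a two-sided 95% interval: 4.35 + 1.960 × 6.01 = 16.1, so it is not met.

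**A two-sided test of no difference is a third question.** hDPP 69/138, dDPP 57/138: the deficit is 8.7 points and the test of no difference gives p = 0.15, yet the 9.2 upper limit is 18.5 and non-inferiority fails. That test does not address the 9.1 null.

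**Scale.** On the odds-ratio scale a 15-point deficit is (0.35/0.65)/(0.50/0.50) = 0.54 at 50% hDPP success, (0.25/0.75)/(0.40/0.60) = 0.50 at 40%, and (0.15/0.85)/(0.30/0.70) = 0.41 at 30%. A logistic coefficient therefore has no single counterpart to the margin.

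**Clustering.** If the 9.4.1 clustering enters the variance, the independence behind 80% no longer holds. The documents give no intraclass correlation. For assumed design effects D in the hDPP arm only, at 50% success and n = 138, the standard error is √(0.25(1 + D)/138). Power at one-sided 5% is then about 78% (D = 1.1), 76% (D = 1.25) and 72% (D = 1.5).

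**The case against.** The strongest reply is that the decision rule is already in the plan. Sections 9.1 to 9.4 are one chapter; 9.1 states the null and margin, and 9.2 states the limit. The 9.3 sentence is general, sits under a heading on analysis populations and gives no alpha, so the specific rule could be taken to prevail. A one-sided 95% limit is also the upper limit of a two-sided 90% interval, which would reconcile the passages. This stands in part: the rule is not missing. But the documents never state that reconciliation or say which passage prevails.

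Two further points largely stand. Section 9.4.7 may be shorthand for the mixed model in 9.4.1. And an ordinary logistic model with treatment alone reproduces the two observed percentages, so an unadjusted analysis gives the risk difference directly. The scale problem therefore applies mainly to the mixed model.

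A reader might infer that the plan would declare non-inferiority from a non-significant two-sided test. With dDPP truly 15 points worse, such a test at 5% would be non-significant in about 29% of trials at 50% hDPP success and 15% at 30%, against about 5% passing under 9.2. No passage proposes that inference, so these rates only illustrate why the two tests are not interchangeable.

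Other 95% intervals do appear, for A1C device accuracy (8.2.2) and for the landmark DPP trial's effect (9.1). Neither concerns this trial's own comparison.

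**Conclusion.** The conflict is real and should be fixed. Section 9.3 as written is incompatible with the criterion that produced 138 and 184 per arm, and the analysis sections do not carry that criterion forward.

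Its size depends on the intended reading. If 9.2 governs, nothing numerical changes: power is 80.2% at 50% success and higher at 30–40%, with independent participants. If a two-sided 95% interval is intended, power at 138 per arm falls to between 70% (50% success) and 78% (30%), and observed results near the margin can change from pass to fail.

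A reader might conclude that the trial is underpowered. The documents do not support that. The lower figures require joining 9.3's wording to a 5% level that 9.2 itself ties to a one-sided limit, and they require the full 25% attrition, which 9.2 calls conservative. With all 184 per arm analysed, power would be 82–88% even under that reading.

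**What to change.** In 9.3, exempt the primary non-inferiority test from the two-sided statement and apply the 9.2 rule: one-sided 5%, reported as a two-sided 90% confidence interval.

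In 9.4.7, state that the primary result is the risk difference, hDPP minus dDPP, with that upper limit; name one model consistent with 9.4.1 and how the risk difference is obtained from it; and state that non-inferiority is declared if the limit is below 15 points.

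If program clustering enters the variance, add to 9.2 that the 80% assumes independent participants and would be lower with clustering.

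Only if the sponsor intends a two-sided 95% interval, say so in 9.2 and restate power for 276 evaluable participants as about 70% at 50% success, 72% at 40%, 74% at 35% and 78% at 30%.

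The cost is protocol and SAP wording, with no added participants or procedures. The stated power is unchanged under the 9.2 rule with independent participants; it becomes less favourable if clustering is carried in the variance or the two-sided 95% interval is chosen.

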## 9.4 STATISTICAL ANALYSES

### 9.4.1 GENERAL APPROACH

This clinical trial will be conducted under a common protocol with analyses conducted on pooled data from both sites. Data analyses will be conducted by a biostatistician. Exploratory data analysis will be performed to examine outliers, characterize the distributions of continuous and categorical measures, and track missing data. Mean, median, and frequency counts will be used to summarize baseline characteristics measured on a continuum, and proportions and frequency counts will be used for categorical measures. Baseline statistical differences in continuous measures between groups will be assessed using unpaired t-tests or Wilcoxon signed rank test, and statistical differences in categorical measures will be assessed using chi-square test or Fisher's Exact test as appropriate.

Between-group differences in primary and secondary outcomes will be evaluated in intention-to-treat analyses using mixed effects logistic regression models to account for potential within-program site clustering. For continuous measures in our secondary analyses, linear regression will be used to analyze the outcomes and for binary measures, logistic regression analyses will be used. Interaction terms will be used in regression models to evaluate effect modification.

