## 4 STUDY DESIGN

### 4.1 OVERALL DESIGN

This study will be a Phase 3, parallel group, 12-month non-inferiority RCT to evaluate whether the Sweetch digital diabetes prevention program (dDPP) is at least as effective as a standard of care control group. The control group participants will receive a referral to a local lifestyle change program with preliminary or full recognition status by the CDC for delivery of an in-person or distance learning (e.g. videoconference) based diabetes prevention program (hDPP).

We use the term effectiveness rather than efficacy as we wish to evaluate the real-world effect of both interventions without aggressive interference on the part of the study team. The primary endpoints across all the study aims will be assessed at 12 months, with secondary endpoints assessed at 6 and 12 months to evaluate the sustainability of the intervention.

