## 6.4 MEASURES TO MINIMIZE BIAS: RANDOMIZATION AND BLINDING

Block stratified randomization by baseline A1C level (5.7% to 6.0% vs. 6.1% to 6.4%) and recruitment site (JHU vs. Reading) will be done to ensure that the groups are balanced with respect to this variable, since higher A1C level at baseline is the strongest risk factor for progression to incident diabetes and potential need for glucose-lowering medications.

For several pragmatic reasons, this will be an open-label trial (i.e. treatment allocation will be unblinded to both participants and the study team). For efficiency, research coordinators conducting the home study visit will also be responsible for randomization and measurement of height and weight. Since the study team members will also need to interact with local DPPs, it would be practically challenging to blind the study team members to treatment assignment. The biostatistician will also be unmasked to treatment assignment and will provide required reports to the DSMB. The study team will have real-time access to all systems log data collected by Sweetch in the form of a dashboard.

Considering that hDPPs enroll participants to their programs on a rolling basis depending on the number of interested participants available to join a new cohort and availability of lifestyle coaches, it is possible that there will be times during the enrollment period where there may be an absence of available hDPPs to accept participants randomized to that arm in a timely fashion.

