#### 9.4.3 BASELINE DESCRIPTIVE STATISTICS

Comparison of baseline characteristics between the intervention group and control groups will be conducted to assess the degree to which randomization was adequately achieved. Demographics (age, race, and gender), socioeconomic status (employment, education), comorbid conditions associated with metabolic syndrome (hypertriglyceridemia, hypertension, etc.) and factors relevant to the primary and secondary outcomes (baseline A1C, weight) will be reported. For normally distributed data, means and SDs will be shown. For non-normally distributed data, median and Interquartile range will be shown.

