#### 9.4.5 COVARIATE ADJUSTMENT

We anticipate that randomization will minimize differences in participant characteristics that may be associated with the primary or secondary endpoints between the two groups. All primary statistical analyses will be unadjusted. However, if we identify differences in participant baseline characteristics, or exposure to potential confounders during the course of the study (e.g. steroid use, antihyperglycemic use), sensitivity analyses will be conducted to include these variables as covariates in multivariable logistic or linear regression models, as appropriate. These adjusted analyses will be viewed as supportive in interpreting the findings of the unadjusted analyses.

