#### 9.4.7 ANALYSIS OF THE PRIMARY EFFICACY ENDPOINT(S)

The primary effectiveness endpoint will be analyzed using an intention to treat approach (ITT) using logistic regression models, where attainment of the CDC's benchmark for type 2 diabetes risk reduction will be the dependent variable and treatment group the

primary exposure variable. Covariate-adjusted models will include any variables that are identified to be statistically significantly different on univariate analysis between the two treatment groups at baseline or over the study period, including use of medications that could influence blood glucose (antihyperglycemics, steroids) and incident diabetes.

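### Section 9.4.1 names a paired rank test (Wilcoxon signed rank) for comparing continuous baseline measures between two independent arms; it should name the Wilcoxon rank-sum (Mann-Whitney) test

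*Combined protocol and SAP*

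**What the plan says.** Section 9.4.1 (General Approach) sets the tests for comparing the arms at baseline: "Baseline statistical differences in continuous measures between groups will be assessed using unpaired t-tests or Wilcoxon signed rank test". For categorical measures it names the chi-square and Fisher's exact tests.

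Section 9.4.3 gives the purpose: "Comparison of baseline characteristics between the intervention group and control groups will be conducted to assess the degree to which randomization was adequately achieved". It also expects some variables to be non-normal, since it provides medians and interquartile ranges for them.

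On design, Section 4.1 states: "This study will be a Phase 3, parallel group, 12-month non-inferiority RCT". Section 6.4 describes blocked randomisation stratified by baseline A1C band and recruitment site. Neither section describes matched pairs.

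Section 9.4.7, on the primary endpoint, adds: "Covariate-adjusted models will include any variables that are identified to be statistically significantly different on univariate analysis between the two treatment groups at baseline", and extends the rule to differences that arise during the study. Section 9.4.5 fixes the standing of such models. Of the main analyses it says "All primary statistical analyses will be unadjusted", and of the adjusted ones "These adjusted analyses will be viewed as supportive in interpreting the findings of the unadjusted analyses".

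**The concern.** The signed rank test works on within-pair differences. A participant in one arm has no partner in the other, so the test does not answer the question that Section 9.4.1 puts to it. The sentence is also inconsistent with itself: it offers an unpaired t-test and a paired rank test as alternatives for the same comparison.

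Two things are at stake, both modest. First, the plan names no valid rank test for the skewed variables that Section 9.4.3 expects. An analyst must either follow the text and be wrong, or run the right test and depart from the written plan. Second, if the Section 9.4.1 tests are also the univariate analysis meant in Section 9.4.7, an invalid p-value could decide whether a skewed continuous baseline variable enters the adjusted model of the primary endpoint.

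**Working it through.** **1. The plan's own figure.** Section 9.2 gives a 5% significance level used with a one-sided 95% confidence limit, 80% power, 50% success in both arms and a 15-point margin.

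- n per arm = (z₀.₉₅ + z₀.₈₀)² × [p(1−p) + p(1−p)] / margin²
- = (1.645 + 0.842)² × (0.25 + 0.25) / 0.15² = 6.185 × 0.5 / 0.0225 = 137.4, rounded up to 138, or 276 in total
- with 25% attrition, 138 / 0.75 = 184 per arm, or 368 in total

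Both figures match the plan. No baseline test enters this formula, so the point does not bear on sample size.

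**2. What each rank test needs.**

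- *Signed rank:* form dᵢ = xᵢ − yᵢ for i = 1 to n, rank the |dᵢ|, and sum the ranks of the positive dᵢ. The index i must refer to the same person, or a matched pair, in both columns, and the columns must be of equal length.
- *Rank-sum:* over all n₁ × n₂ cross-arm comparisons, count how often xᵢ exceeds yⱼ, with ties counted as one half. It needs neither pairing nor equal arms.

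Sections 4.1 and 6.4 describe independent arms, so only the second fits. Equal arm sizes are not assured either. Stratification by two A1C bands and two sites gives 2 × 2 = 4 strata, any of which may end on an incomplete block, and baseline values may be missing.

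**3. What happens if the text is followed literally.** These are illustrations on simulated data, not estimates for this trial.

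- *Unequal arms (assumed 184 and 180):* the signed rank test cannot be computed.
- *Equal arms (184 each), no true difference, with a dataset picked because it lay near the 5% line (rank-sum p = 0.049):* pairing by row over 2,000 random orders gave signed rank p-values from 0.021 to 0.128 (central 95%). In 39% of orders p was below 0.05.
- *Equal arms (184 each), values drawn with a true mean difference of 0.2 standard deviations, rank-sum p = 0.0003:* every one of 2,000 orders gave p below 0.05, the largest being 0.003.

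The dependence on row order therefore matters for borderline variables and not for clear differences.

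**4. How far the error travels.**

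- *Baseline comparison (9.4.1, 9.4.3):* direct, but only for continuous variables judged non-normal. The t-test, chi-square and Fisher's exact tests are suitable.
- *Covariate entry (9.4.7):* indirect. The section requires significance on univariate analysis but names no test and no threshold, and does not refer back to 9.4.1. The link is inferred from 9.4.1 being the only place where tests for between-arm baseline differences are named.
- *Covariates that 9.4.7 mentions by example:* medication use and incident diabetes. These are yes/no variables arising during the study, and no rank test on continuous baseline data would select them.
- *Primary non-inferiority result:* not reached, because Sections 9.3 and 9.4.5 make it unadjusted.

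**The case against.** The strongest reply is that this is a slip of name with an obvious meaning. The sentence concerns differences between groups and sets the rank test beside an unpaired t-test, so the two-sample Wilcoxon test was almost certainly intended. A biostatistician will run the analysis, nobody is likely to pair strangers by row, and unequal arms would expose the error at once. The clearly continuous variables listed in Section 9.4.3 are age, baseline A1C and weight. A1C band is a stratification factor, and the t-test tolerates moderate skew with 184 planned per arm. The documents do not show that any named variable would need the rank test.

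Most of that stands, and it is why the point is minor. It does not make the text right. The sentence is an operative analysis rule, no other section corrects it, and Section 9.4.3 expects non-normal variables.

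A reader might also infer that an invalid test chooses the covariates of the primary model, and so threatens the non-inferiority conclusion. The documents do not support that. Sections 9.3 and 9.4.5 make the primary analysis unadjusted and treat adjusted models as supportive. Section 9.4.7 does not tie its univariate analysis to the tests in Section 9.4.1. Only the weaker statement is defensible: the misnamed test may influence which skewed continuous baseline variables enter a supportive model.

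**Conclusion.** The test named in Section 9.4.1 is wrong for the comparison described, and this can be said with high confidence from the text alone. The consequence is small: a missing valid rank test for non-normal continuous baseline variables and, by inference, possible arbitrariness in whether such a variable enters the supportive adjusted model of the primary endpoint. That second part assumes that Section 9.4.1 supplies the tests for Section 9.4.7, that at least one continuous baseline variable is judged non-normal, and that the text is followed literally. The primary result and the sample size do not change.

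**What to change.** In Section 9.4.1, replace the Wilcoxon signed rank test with the Wilcoxon rank-sum (Mann-Whitney) test. While that text is open, Section 9.4.7 could state which tests, if any, govern covariate entry, or could list the covariates in advance, for example the stratification factors in Section 6.4. Whether covariates should be chosen by significance at all is a separate question that the rename does not settle. The cost is a wording change in the plan, with no effect on data collection, sample size or conduct.

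### The 80% power assumes independent participants although section 9.4.1 plans to model hDPP programme clustering, and section 9.4.7 names a primary model without it

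*Combined protocol and SAP*

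**What the plan says.** Section 9.2 sizes the trial "with a significance level (alpha) of 5% and 80% power, and assuming 50% of the participants achieve the primary outcome in both arms". It concludes that "138 participants are required to enroll in each of the two arms" and inflates this to 184 per arm for 25% attrition. The criterion is stated as "80% sure that the upper limit of a one-sided 95% confidence interval will exclude a difference in favor of the hDPP of more than 15" percentage points. No ICC, number of programmes, programme size or design effect appears. The only robustness claimed is to other values of the hDPP success rate.

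Section 9.4.1 says that between-group differences in primary and secondary outcomes will be evaluated with "mixed effects logistic regression models to account for potential within-program site clustering". Section 9.4.7, which is specific to the primary endpoint, says: "The primary effectiveness endpoint will be analyzed using an intention to treat approach (ITT) using logistic regression models". There, treatment group is the primary exposure and no programme term is named. Section 9.3 adds: "All primary statistical analyses of effectiveness measures will be unadjusted and two-sided tests of significance will be used".

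Section 9.1 gives success rates among completers in five participating hDPPs, described as a subset. These range from 47% to 60% for 5% weight loss and from 29% to 80% for 4% weight loss with activity. The section offers this variability as part of the justification for the 15-point margin. Section 9.4.6 plans to explore hDPP outcomes by programme site.

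**The concern.** hDPP participants are taught in group programmes. dDPP participants use an app and belong to no programme. The design is therefore partially nested: outcomes may be correlated within programmes in one arm only. A calculation that is silent on this sets the correlation to zero, yet section 9.4.1 plans a model because it may not be zero, and section 9.1 uses between-programme variability to support the margin.

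Two things are at stake. If clustering is modelled, the standard error grows and power falls below the independent-data figure. If it is not modelled, the confidence bound sits too close to the estimate, and in this trial that error favours declaring the app non-inferior.

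The plan also leaves the cluster undefined. It does not say how dDPP participants enter a programme-level model. Nor does it say how to place hDPP participants who never attend (foreseen in section 5.6.2.2) or who change programme after the core phase (allowed in section 6.2). Finally, the hypothesis in section 9.1 is a difference of 15 percentage points, and neither logistic model gives that difference directly. Because section 6.4 leaves the biostatistician unmasked, the choice between models should not stay open.

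**Working it through.** **Inputs from the plan.** One-sided alpha 5%, power 80%, 50% success in both arms and 138 analysable per arm (section 9.2); margin 15 points (section 9.1); expected ITT success in the hDPP arm 30-40% (section 9.1).

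**Assumptions, not in the plan.** ICC 0.01 to 0.05; k = 5, 10 or 20 equal-sized programmes; clustering in the hDPP arm only.

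**1. The plan's own figure.** n = (1.645 + 0.842)² × [0.5×0.5 + 0.5×0.5] / 0.15² = 137.4, so 138 per arm. Then 138 / 0.75 = 184. Both match section 9.2. Power at 138 per arm is 80.2%. The match requires a design effect of 1, so no clustering allowance is present.

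**2. Power with clustering in the hDPP arm.**

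DE = 1 + (138/k − 1) × ICC

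SE = √[p(1 − p)(1 + DE)/138]

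Power = Φ(0.15/SE − 1.645)

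Example, k = 10, ICC = 0.02, p = 0.50: DE = 1 + 12.8 × 0.02 = 1.256; SE = √(0.25 × 2.256/138) = 0.0639; power = Φ(2.346 − 1.645) = 75.9%.

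| Success rate | Programmes | ICC 0.01 | 0.0125 | 0.02 | 0.05 |
|---|---|---|---|---|---|
| 50% | 20 | 79.1% | 78.9% | 78.1% | 75.2% |
| 50% | 10 | 78.0% | 77.4% | 75.9% | 70.0% |
| 50% | 5 | 75.7% | 74.6% | 71.6% | 61.3% |
| 35% | 20 | 82.4% | 82.1% | 81.4% | 78.6% |
| 35% | 10 | 81.3% | 80.8% | 79.2% | 73.5% |
| 35% | 5 | 79.1% | 78.1% | 75.1% | 64.8% |

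Without clustering, power is 81.6%, 83.3% and 85.9% at 40%, 35% and 30% success. That slack absorbs a small ICC. These figures use a normal reference; a small-sample correction would lower them somewhat.

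**3. Error if clustering is ignored.** With equal variances, the actual one-sided error is 1 − Φ(1.645 × √[2/(1 + DE)]). For k = 10 and ICC 0.05, DE = 1.64 and the error is 1 − Φ(1.432) = 7.6%. Over ICC 0.0125 to 0.05 it runs from 5.7% to 7.6% with 10 programmes and from 5.3% to 6.2% with 20. Setting the dDPP rate at 35% against 50%, the boundary of the null, changes these upper ends only to 7.7% and 6.3%.

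**4. What the programme ranges imply.** For five values, SD ≈ range/2.326. The 47-60% range gives SD 0.13/2.326 = 0.056 and ICC 0.056²/0.25 ≈ 0.0125. The 29-80% range gives SD 0.219 and ICC ≈ 0.19. Both still contain sampling noise. With 80 completers per programme (an assumption), noise alone has SD √(0.25/80) = 0.056, which accounts for the whole of the first range.

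**5. Non-attendance.** Section 2.2 gives about 35% attendance among those referred, as background. If only that fraction f were correlated, DE = 1 + f(f × 138/k − 1) × ICC. At ICC 0.02 and 50% success, power is then 79.1% (k = 5), 79.7% (10) or 80.0% (20), a loss of about one point or less.

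**The case against.** The strongest reply is that nothing in section 9.2 is miscalculated. The 138 and 184 reproduce exactly, section 9.4.1 calls the clustering only potential, and 50% was chosen deliberately as the most demanding success rate when 30-40% is expected. Section 9.4.7 may be shorthand for the 9.4.1 model: it omits the programme effect without excluding it. Most of this stands, and it limits the claim.

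A reader might infer any of the following, and the documents support none of them:

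- *The 80% power, or the 5% error rate, is wrong.* It is correct for its stated inputs. Without an ICC or programme count, no shortfall can be demonstrated.
- *80% power fails at every plausible ICC.* At 35% success, 10 programmes and ICC 0.0125, power is 80.8%.
- *The five-programme figures are the likely case.* Section 9.1 calls the five a subset, and section 6.2 allows programmes to be added.
- *The 29-80% range shows strong clustering of the primary endpoint.* It concerns one component, among completers, as reported by programmes. The trial endpoint is a composite with activity measured by ActiGraph.
- *The plan wrongly puts a programme effect on dDPP participants.* It does not say so; the model is under-specified.

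The reply does not remove the missing allowance, the two differently described primary models or the undefined cluster. The 35% attendance figure is also background and not a trial assumption; here the study pays all programme costs (section 5.6.2.2).

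**Conclusion.** The point holds in a limited form. The 80% is a figure for independent participants. Under the model in section 9.4.1 it is unsupported and may be overstated, by about 1 to 10 points with 10 to 20 programmes at 50% success, and by little or nothing at the expected success rates if the ICC is small. The analysis side matters more: section 9.4.7 followed as written gives an anti-conservative non-inferiority bound under any positive ICC, by an amount that is modest at small ICCs and grows with the ICC and with programme size. These sizes rest on assumed ICCs, assumed equal-sized programmes, 138 analysable per arm and the one-sided 5% level of section 9.2. The reference to two-sided tests in section 9.3 is a separate matter and is not used here.

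**What to change.** - **Section 9.2:** state that no clustering allowance was made, and tabulate power over a range of ICCs and programme numbers at 30-50% success.
- **Sections 9.4.1 and 9.4.7:** name the same single primary analysis. It should estimate the risk difference for comparison with the 15-point margin and allow for clustering in the hDPP arm only. Two suitable forms are a small-sample cluster-robust variance, or a random programme effect in the hDPP arm only with a marginal risk difference derived from it.
- **Cluster definition:** use the programme to which the participant was first referred, including those who never attend and those who later switch. Treat each dDPP participant as a cluster of one.

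The cost is analysis-plan wording, settled before outcomes are compared by arm. No added enrolment is proposed. The stated power becomes slightly less favourable and the confidence interval slightly wider.
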